**Table 2: Grid search result for threshold value of moderate vs high risks**

Possible Threshold values for high risk vs moderate risk	Youden's Index	SE	SP	PPV	NPV	Rank of Youden's Index	Flag for solution space
0	XXX	XXX	XXX	XXX	XXX		
...							
511	XXX	XXX	XXX	XXX	XXX	10/1000	Yes
512	XXX	XXX	XXX	XXX	XXX	100/1000	Yes
513	XXX	XXX	XXX	XXX	XXX	200/1000	No
...							
999	XXX	XXX	XXX	XXX	XXX		

In the second step, the final optimal cut-points threshold values will be selected from the solution space, with clinical justification such that the balance between sensitivity and specificity is achieved. For example, a cut-off point of 20 is selected for low risk vs moderate risk group based upon clinician's justification. This framework will integrate clinical knowledge into purely data-driven techniques.

Assuming the acceptable SE and SP are 0.8 for both cutoffs (low vs moderate/high and low/moderate vs high), with a sample size of 750 patients in the training data set, the width of 95% confidence intervals of SE and SP estimations are 0.026 and 0.056 for the classification cutoffs that predict low risk vs moderate/high (prevalence 82.9% vs 17.1%). For predicting low/moderate risk vs high risk (prevalence 2.1% vs 97.9%), the width of confidence intervals for SE and SP are 0.143 and 0.024, respectively. The narrow confidence intervals imply relatively high precision for the SE and SP estimations, which will be used to support clinicians' decision making.

The final selected cut-points threshold values will be validated with an independent testing data set in Aim 2.

**Statistical Aim 2 – To validate discriminative ability of NS metric (with the established risk levels of low, moderate, and high) as a clinical measure to evaluate opioid use risk level.**

The second primary aim of the project is to evaluate the concurrent validity of the NS metric with the established risk levels of low, moderate, and high. Classification accuracy will be evaluated with an independent testing data set, and WHO ASSIST will be used as the gold standard to define actual risk levels for patients. The agreement level of risk groups defined by NS metric and WHO ASSIST will be descriptively summarized with a confusion matrix, see **Table 3**. Each row of the matrix represents the instances and percentages in a predicted risk level while each column represents the instances in an actual risk level.

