The study will be powered to the least prevalent but most severe condition among potential patients. Based on the allocation ratio of the national rate of prescription opioid use disorder (POUD) among those prescribed opioid medications in the last year, the prevalence of Poud is 2.1%. A sample of approximately 1,523 (32 positive group) achieves 97.68% power to detect a difference of 0.2 between the area under the ROC curve (AUC) under the null hypothesis of 0.5 and the alternative hypothesis of 0.7 using a two-sided z-test at a significance level of 0.050.

The Completer Population (both training and testing set) will be used to assess the overall discrimination ability of NS metric.

*To determine cut-point threshold values for NS total score:*

The objective is to select the optimal cut-points threshold for NS metric to define low, moderate and high risk groups. We will use a hybrid framework where we can make use of the data driven methods to support the clinician's final decision making. Only the training data set will be used in this portion of analysis.

In the first step, the solution space (a subset of optimum choices of cut-point threshold values) will be identified with the following grid search approach: for each pair of risk groups, for example, low risk vs moderate risk, calculate the following performance measurements for each possible cut-point threshold value:

- Sensitivity (SE)

$$SE = \frac{\text{True Positive Rate}}{\text{True Positive Rate} + \text{False Negative Rate}}$$

- Specificity (SP)

$$SP = \frac{\text{True Negative Rate}}{\text{True Negative Rate} + \text{False Positive Rate}}$$

- Positive Predictive Value (PPV): probability that the risk level is present (based on WHO ASSIST) when the result with NS metric is positive.
- Negative Predictive Value (NPV): probability that the risk level is not present (based on WHO ASSIST) when the test result with NS metric is negative.
- Youden's index:

$$\text{Youden's Index} = SE + SP - 1$$

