	Figure 3.2	CP	NS metric ROC curve for discriminating moderate risk vs low risk opioid misuse patients defined by WHO ASSIST opioid items.
	Figure 3.3	CP	NS metric ROC curve for discriminating high risk vs moderate risk opioid misuse patients defined by WHO ASSIST opioid items, by gender
	Figure 3.4	CP	NS metric ROC curve for discriminating moderate risk vs low risk opioid misuse patients defined by WHO ASSIST opioid items, by gender
	Table 3.5	CP	Summary of AUC of ROC curve
	Table 3.6	CP	Summary of AUC of ROC curve, by gender
	Table 3.7	CP - Training	Summary of grid search: ROC analysis results for all possible cut-off threshold values of high risk vs moderate risk with NS metric.
	Table 3.8	CP - Training	Summary of grid search: ROC analysis results for all possible cut-off threshold values of moderate risk vs low risk with NS metric.
	Table 3.9	CP - Training	Summary of grid search: ROC analysis results for all possible cut-off threshold values of high risk vs moderate risk with NS metric by gender
	Table 3.10	CP - Training	Summary of grid search: ROC analysis results for all possible cut-off threshold values of moderate risk vs low risk with NS metric by gender
	Figure 3.11	CP - Training	NS metric ROC curve for discriminating high risk vs moderate risk opioid misuse patients defined by WHO ASSIST opioid items, with training data set.
	Figure 3.12	CP - Training	NS metric ROC curve for discriminating moderate risk vs low risk opioid misuse patients defined by WHO ASSIST opioid items, with training data set.
	Figure 3.13	CP -	NS metric ROC curve for discriminating high risk

Section	Table/Figure #	Analysis Population	Title
		Training	vs moderate risk opioid misuse patients defined by WHO ASSIST opioid items, with training data set, by gender.
	Figure 3.14	CP - Training	NS metric ROC curve for discriminating moderate risk vs low risk opioid misuse patients defined by WHO ASSIST opioid items, with training data set, by gender.
	Figure 3.15	CP- Training	Plot of Kappa Coefficient for NS metric vs WHO Assist, for all possible threshold values in selected solution space
	Figure 3.16	CP - Training	Plot of Kappa Coefficient for NS metric vs WHO Assist, for all possible threshold values in selected solution space, by gender
	Figure 3.17	CP - Training	Plot of Spearman Correlation Coefficient for NS metric vs WHO Assist, for all possible threshold values in selected solution space

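### The stated confidence-interval widths for sensitivity and specificity are too small by a factor of about 2.5 to 3, and the claim of high precision fails for sensitivity at the high-risk cut-off

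*SAP*

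**What the plan says.** The paragraph after Table 2 in SAP section 3.5 (Aim 1) sets SE and SP to 0.8 for "both cutoffs (low vs moderate/high and low/moderate vs high", with 750 patients in the training set. For low against moderate/high (82.9% against 17.1%), it says "the width of 95% confidence intervals of SE and SP estimations are 0.026 and 0.056". For the other cut-off it says "the width of confidence intervals for SE and SP are 0.143 and 0.024". It then concludes: "The narrow confidence intervals imply relatively high precision for the SE and SP estimations", and adds that the estimates will support the clinicians' choice of cut-points. It names no interval method.

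The search itself is described differently. Earlier in section 3.5 the instruction is "for each pair of risk groups, for example, low risk vs moderate risk, calculate the following performance measurements". Table 2 is titled for moderate against high risk. The Appendix 1 training-set shells follow the same pattern, for example "ROC analysis results for all possible cut-off threshold values of high risk vs moderate risk with NS metric".

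The 2.1% comes from "the national rate of prescription opioid use disorder (POUD) among those prescribed opioid medications in the last year". It is not a measured frequency of high risk on the WHO ASSIST in this population.

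**The concern.** There are three faults.

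- **Widths.** A 95% interval only 0.143 wide around a proportion of 0.8 is not credible when the group holds about 16 people. The other three figures also look too small for their group sizes.
- **Denominators.** The widths use cumulative splits of the whole training set, while the search they are meant to support compares adjacent groups only.
- **Labelling.** The positive class is not stated for either cut-off. The SE figure belongs to the low-risk group at one cut-off and to the high-risk group at the other. The second bracket also lists its prevalences in the reverse order of its labels: "For predicting low/moderate risk vs high risk (prevalence 2.1% vs 97.9"%.

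High risk is the condition to which the study is powered. Clinicians told that sensitivity there is known precisely could put far more weight on it than the data will bear.

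**Working it through.** **Inputs** (all from SAP section 3.5): SE = SP = 0.8; 750 training patients; prevalences 82.9%, 17.1%, 2.1% and 97.9%.

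**Group sizes**
- Low: 750 × 0.829 = 621.8, about 622
- Moderate/high: 750 × 0.171 = 128.3, about 128
- High: 750 × 0.021 = 15.75, so 15 or 16
- Low/moderate: 750 × 0.979 = 734.3, about 734
- Moderate alone: 17.1% − 2.1% = 15.0%; 750 × 0.150 = 112.5, about 112

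**Where the stated figures could come from.** One rule gives all four: the exact (Clopper-Pearson) one-sided 95% upper limit minus 0.8, that is Beta⁻¹(0.95; 0.8n + 1, 0.2n) − 0.8. It yields 0.0261 (n = 622), 0.0563 (n = 128), 0.1432 (n = 15) and 0.0240 (n = 734). At n = 16 the third value would be 0.1399. This is the distance to one limit only, and on the shorter side: at n = 15 the matching lower distance is 0.240. The SAP does not say that this rule was used, so the origin is an inference. The mismatch below does not depend on it.

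**Two-sided 95% widths at 0.8**
- Exact: Beta⁻¹(0.975; 0.8n + 1, 0.2n) − Beta⁻¹(0.025; 0.8n, 0.2n + 1)
- Wald: 2 × 1.96 × √(0.8 × 0.2 / n)
- Wilson: the score interval

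| Group (n) | Stated | Exact limits | Exact width | Wald width | Wilson width | Wald half-width | Exact / stated |
|---|---|---|---|---|---|---|---|
| Low (622) | 0.026 | 0.766–0.831 | 0.064 | 0.063 | 0.063 | 0.031 | 2.5 |
| Moderate/high (128) | 0.056 | 0.720–0.866 | 0.145 | 0.139 | 0.138 | 0.069 | 2.6 |
| High (15) | 0.143 | 0.519–0.957 | 0.438 | 0.405 | 0.381 | 0.202 | 3.1 |
| High (16) | 0.143 | 0.530–0.954 | 0.424 | 0.392 | 0.371 | 0.196 | 3.0 |
| Low/moderate (734) | 0.024 | 0.769–0.828 | 0.059 | 0.058 | 0.058 | 0.029 | 2.5 |

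No full width or half-width matches a stated figure. These are planning values; except for 12 of 15, the counts that 0.8 implies are not whole numbers. The nearest whole counts give similar limits, for example 0.544–0.960 for 13 of 16.

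A full width of 0.143 at 0.8 would need about 121 (Wald) to 133 (exact) high-risk patients.

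**Pairwise denominators, higher risk as positive.** SE for low against moderate and SP for moderate against high both rest on the moderate group, n about 112. The exact limits are 0.714–0.870, width 0.156 (Wald 0.148, Wilson 0.147). The other two estimates keep their group sizes (low about 622, high 15 or 16).

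**Testing set.** 1,523 × 0.021 = 32 high-risk patients. The 1:1 split, stratified by risk level, puts about 16 in each half.

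**If the 2.1% is wrong.** Assumed prevalences, with exact limits for high-risk sensitivity at the attainable count nearest 0.8:
- 1% (6 of 8): 0.35–0.97
- 3% (18 of 22): 0.60–0.95
- 5% (30 of 38): 0.63–0.90

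**The case against.** **Consequence is limited.** The sample size comes from the AUC calculation, and cut-points come from Youden's index plus clinical justification. No decision rule uses these widths. This is true, and it keeps the point to a correction of figures and one conclusion.

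**The two splits can coexist.** One may search between adjacent groups and then state precision for the cut-off as applied to everyone, which is how the three-level confusion matrix in Table 3 will be filled. This is a fair reading, but the SAP does not say so. The right request is to state which is meant, not to assume that the cumulative split is wrong. Only two denominators change, and high-risk sensitivity is not among them. For SP at the high-risk cut-off, the overall ratio of 0.156 to 0.024 (6.5) combines two effects: the type of width (0.059 / 0.024, about 2.5) and the choice of split (0.156 / 0.059, about 2.6).

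**The positive class can be inferred.** Higher scores mean higher risk, and PPV is defined by the risk level being present. On that reading the SE and SP figures at the first cut-off appear to be swapped, so a definition is still needed.

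**The training limits may flatter.** The cut-point is chosen in the same patients, so observed training sensitivity tends to be optimistic. This caveat adds to the concern.

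**Conclusion.** The concern holds. All four figures are wrong as labelled, whether read as two-sided 95% widths or as half-widths, by the exact, Wald or Wilson method. True widths are about 2.5 to 3 times those stated.

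The claim of relatively high precision is not supported for high-risk sensitivity. Its interval is 0.37 to 0.44 wide across methods, under either split. The testing set provides a separate estimate, but from about the same number of high-risk patients, so it is no more precise.

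This rests on the SAP's assumed 0.8 and 2.1%. At an assumed 5% prevalence the interval would still be about 0.27 wide (0.90 − 0.63). The documents set no criterion for a narrow interval, so no judgement is made on the other three estimates; their figures simply need to be right. The conflict between pairwise and cumulative splits is real and needs a stated choice.

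**What to change.** In SAP section 3.5 (Aim 1):

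1. Define the positive class for both cut-offs, and list prevalences in the same order as the labels.
2. State whether SE and SP are computed pairwise or cumulatively, and make the grid-search text, Table 2, the precision paragraph and the Appendix 1 shells agree.
3. Replace the four figures with two-sided 95% limits and name the method. Exact planning values at 0.80, with higher risk as positive:

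| Split | Cut-off | SE | SP |
|---|---|---|---|
| Pairwise | Low vs moderate | 0.71–0.87 (n about 112) | 0.77–0.83 (n about 622) |
| Pairwise | Moderate vs high | 0.52–0.96 (n = 15); 0.53–0.95 (n = 16) | 0.71–0.87 (n about 112) |
| Cumulative | Low vs moderate/high | 0.72–0.87 (n about 128) | 0.77–0.83 (n about 622) |
| Cumulative | Low/moderate vs high | 0.52–0.96 (n = 15); 0.53–0.95 (n = 16) | 0.77–0.83 (n about 734) |

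4. Withdraw the precision statement for high-risk sensitivity. Suggested text: *If the assumed 2.1% prevalence holds, sensitivity at the high-risk cut-off rests on about 15–16 patients in each of the training and testing sets; an observed 0.80 would be compatible with roughly 0.52 to 0.96.* A short note that training estimates are optimistic, because the cut-point is selected in the same patients, would help.

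The cost is one rewritten paragraph and one clarification. Sample size and design do not change. The stated precision for high-risk sensitivity becomes less favourable.

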**Table 3. Confusion matrix**

Predicted risk levels defined by NS metric		Actual risk levels defined by WHO ASSIST		
		Low risk level	Moderate risk level	High risk level
Low risk level		XXX(XX.XX%)	XX(XX.XX%)	XX(XX.XX%)
Moderate risk level		XX(XX.XX%)	XX(XX.XX%)	XX(XX.XX%)
High risk level		XX(XX.XX%)	XX(XX.XX%)	XX(XX.XX%)

Cohen's Kappa Coefficient will be used to evaluate agreement between the two metrics. The following scale will be used to assess level of agreement: 0-0.2=slight, 0.21-0.4=fair, 0.41-0.6=moderate, 0.61-0.8=substantial, and 0.81-1=near perfect. We expect the NS metric will demonstrate at least moderate ( $\geq 0.40$ ) agreement with the gold-standard risk categories, and a sample size of 750 patients and prevalence of 2.1% (for high risk level) will achieve 99.8% power with a significance level of 0.05 in a test of H0:  $\text{Kappa} \leq 0.4$  vs. H1:  $\text{Kappa} > 0.4$ .

Agreement between NS metric and WHO ASSIST will also be evaluated via Spearman Correlation based upon risk levels (1 for low risk, 2 for moderate risk, and 3 for high risk for both NS metric and WHO ASSIST). The following scale will be used to assess level of agreement: 0-0.3 = low degree, 0.3-0.5 = moderate degree, 0.5-1 = high degree.

An ordinal logistic regression model will be built to estimate the magnitude of association between the metrics, while controlling for other relevant risk factors. In the ordinal logistic regression, WHO ASSIST risk levels will be considered as response variable, and regression covariates will include NS metric, and other relevant indicators known to be associated with opioid-related risk, including: sex, pain, general health status, depression, and substance use history (**Table 1**). The association between WHO ASSIST and NS metric will be estimated by odds ratios, and Wald statistics will be used to examine the association at a 0.05 significance level.

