9.4 Significance Testing

The analyses will be conducted using a two-sided test with a type I error rate of 5%.

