### 1.2 STUDY OBJECTIVES

The goal of the study is to validate NS metric as Prescription Drug Monitoring Program-based instrument to discriminate between low, moderate, and high-risk opioid use disorder. The World Health Organization Alcohol, Smoking, and Substance Involvement Screening Test (WHO ASSIST) will be used as the gold standard instrument that defines patient risk levels. No intervention or hypothesis will be tested.

There are 2 statistical Aims in the project:

**Aim 1:** To assess the overall ability of NS metric to discriminate between opioid use risk levels and to determine cut-point thresholds for NS metric total score to classify patients into low, moderate, and high risk groups.

**Aim 2:** To validate the NS metric classifier (with selected cut-point threshold values from Aim 1 as a clinical measure to evaluate patients’ opioid risk level, with WHO ASSIST as the gold standard to which the NS metric is compared.

Other exploratory statistical Aims include:

- To explore the association between NS metric and other indicators of opioid use risk, such as: the Tobacco, Alcohol, Prescription medication and other Substances (TAPS) Tool; a positive misuse indication from the Prescription Opioid Misuse Index (POMI); and history of opioid overdose.
- To collect validity data on the TAPS tool in a large sample of individuals filling opioid pain medications.

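### The 99.8% power for the Aim 2 kappa test names no alternative kappa; against the printed null it needs a true three-level kappa of about 0.58 to 0.60, not the expected 0.40

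*SAP*

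**What the plan says.** SAP 3.5 introduces Aim 2 with "The second primary aim of the project is to evaluate the concurrent validity of the NS metric". Agreement between NS and WHO ASSIST risk levels goes into a 3×3 confusion matrix (Table 3) and is summarised by Cohen's kappa in the testing half of the sample. Kappa is read on the scale "0-0.2=slight, 0.21-0.4=fair, 0.41-0.6=moderate, 0.61-0.8=substantial, and 0.81-1=near perfect".

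The power statement follows: "We expect the NS metric will demonstrate at least moderate" agreement, glossed as 0.40 or more, and "a sample size of 750 patients and prevalence of 2.1% (for high risk level) will achieve 99.8% power" at a significance level of 0.05, with null kappa ≤ 0.4 and alternative kappa > 0.4. No other kappa value is offered as an expectation in the SAP or the protocol.

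Three other passages bear on it:

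- Under Aim 1, the SAP works out interval widths for the training set: "Assuming the acceptable SE and SP are 0.8 for both cutoffs (low vs moderate/high and low/moderate vs high"), with prevalences of 82.9% vs 17.1% and 2.1% vs 97.9%.
- Protocol 9.4 sets a "two-sided test with a type I error rate of 5" per cent for the analyses, whereas the kappa hypotheses are written in one direction.
- SAP 1.2 states "No intervention or hypothesis will be tested".

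**The concern.** Power is defined only at a stated alternative, and this statement has none. The AUC power statement in the same section does give its null (0.5), its alternative (0.7) and a two-sided test, so the kappa sentence lacks what the SAP supplies elsewhere. The one expectation printed is the boundary of the null. On the SAP's own scale, 0.40 is also the top of the fair band, not the start of the moderate one.

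The number of categories is unclear too. Table 3 has three levels, but the power sentence quotes only the high-risk prevalence.

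What is at stake is how the result is read. Someone told that power was 99.8% could take a testing-set kappa below 0.40 as strong evidence against the NS metric. If the true kappa were 0.45 or 0.50, failing to show kappa above 0.40 would be a common outcome of chance.

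**Working it through.** **Inputs.** n = 750, α = 0.05, null kappa 0.40 and high-risk prevalence 2.1% come from the SAP's kappa paragraph. Low risk of 82.9% comes from the Aim 1 precision paragraph, so moderate risk = 17.1 − 2.1 = 15.0%. Combining the two prevalences into one three-level split is an assumption. So is giving the NS metric the same margins as WHO ASSIST.

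**Method.** Large-sample z-test for kappa with the Fleiss-Cohen-Everitt variance:

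V = {Σ p_ii[1 − (r_i + c_i)(1 − κ)]² + (1 − κ)² Σ_{i≠j} p_ij(c_i + r_j)² − [κ − p_e(1 − κ)]²} / (1 − p_e)²

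Power = Φ{[√n(κ1 − κ0) − z√V0] / √V1}, with z = 1.645 one-sided or 1.960 two-sided (upper tail).

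Cells are κ × (diagonal margins) + (1 − κ) × (product of margins).

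**The plan's figure.** 99.8% cannot be reproduced forwards, because κ1 is missing. At κ1 = κ0 = 0.40, power is 5% one-sided or 2.5% in the upper tail of a two-sided test. The remaining step is to solve backwards.

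**Three levels (82.9/15.0/2.1%).** p_e = 0.829² + 0.150² + 0.021² = 0.710; V0 = 1.357 at 0.40; √750 = 27.39.

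- κ1 = 0.50, two-sided: V1 = 1.271; (2.739 − 1.960 × 1.165)/1.127 = 0.40; power 66%.
- κ1 = 0.595, two-sided: V1 = 1.125; (5.340 − 2.283)/1.060 = 2.88; power 99.8%.

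| True kappa | Three-level, one-/two-sided | Two-level at 2.1%, one-/two-sided |
|---|---|---|
| 0.40 | 5% / 2.5% | 5% / 2.5% |
| 0.45 | 32% / 21% | not needed here |
| 0.50 | 77% / 66% | 22% / 14% |
| 0.55 | 98% / 95% | not needed here |
| 0.60 | 99.96% / 99.88% | 56% / 43% |
| Kappa needed for 99.8% | 0.583 / 0.595 | 0.807 / 0.830 |

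Using the alternative variance in the critical value as well lowers the kappa needed to 0.578/0.588 (three-level) and 0.775/0.790 (two-level). A 5,000-run simulation of the three-level case gave 99.6%/99.3% at 0.58 and 99.9%/99.7% at 0.60.

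**Sensitivity of the 0.58 to 0.60.** With other NS margins the kappa needed is about 0.55 to 0.60. With moderate prevalence from 8% to 25% it is about 0.56 to 0.64. A goodness-of-fit power formula gives 0.62 to 0.63. All lie well above 0.40.

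**What sensitivity and specificity of 0.8 would imply.** Take exactly 0.8 at both cumulative cut-offs.

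- NS low and ASSIST low: 0.8 × 0.829 = 0.6632. NS low in all: 0.6632 + 0.2 × 0.171 = 0.6974.
- NS high and ASSIST high: 0.8 × 0.021 = 0.0168. NS high in all: 0.0168 + 0.2 × 0.979 = 0.2126.
- NS moderate: 1 − 0.6974 − 0.2126 = 0.0900.
- p_e = 0.829 × 0.6974 + 0.150 × 0.0900 + 0.021 × 0.2126 = 0.596.
- The moderate/moderate cell can be anything from 0 to 0.0900, so observed agreement runs from 0.680 to 0.770.
- Kappa runs from (0.680 − 0.596)/0.404 = 0.21 to (0.770 − 0.596)/0.404 = 0.43.

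At the upper end the standard error is 0.031, and (0.4305 − 0.40)/0.0314 = 0.97. Power is Φ(0.97 − 1.645) = 25% one-sided and Φ(0.97 − 1.96) = 16% two-sided, and a simulation of 20,000 runs agrees.

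**Precision at n = 750.** The 95% half-width, 1.96√(V/750), at kappa 0.40/0.50/0.60 is 0.083/0.081/0.076 for three levels and 0.220/0.216/0.204 for two levels at 2.1%.

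**The case against.** The strongest reply is that this is a one-line omission. Keeping the printed null and taking 0.60, the top of the SAP's moderate band, gives 99.88% two-sided for three levels. An unstated alternative near 0.60 would therefore explain the figure without any error. The sample size rests on the AUC, no decision depends on 0.40, SAP 1.2 says nothing is tested, and kappa is otherwise read on a descriptive scale. All of that stands, and it limits the consequence to a stated figure and its interpretation. It does not make the sentence usable: a reader who takes the stated expectation of 0.40 or more at face value is told 99.8% where the calculation gives a few per cent.

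The range of 0.58 to 0.60 does depend on equal margins. On the unequal margins that equal sensitivity and specificity produce, about 0.555 two-sided is enough. Hence the wider range of roughly 0.55 to 0.64.

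Three stronger readings are tempting and should not be drawn.

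- *That a null below 0.4 was used.* A two-level kappa at 2.1% with null 0 and alternative 0.40 gives 99.83% two-sided, but only 94.6% with the alternative variance. Three levels with 0.2 against 0.4 give 99.74%. Neither null is printed, and an alternative of 0.60 against the printed null fits about as well. The documents cannot settle it.
- *That the study's power is 25%/16%.* The 0.8 is an assumption for training-set interval widths, not a design value for kappa. The ceiling applies only to three levels and exactly 0.8 at both cut-offs; a two-level kappa at 17.1% prevalence would be about 0.46.
- *That a kappa of 0.60 is out of reach.* Higher accuracy permits higher kappa, and nothing in the documents rules it out.

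**Conclusion.** The concern holds. The 99.8% does not follow from the inputs printed with it. At the one expectation given, 0.40, power is the significance level. Against the printed null, 99.8% needs a true kappa of about 0.58 (one-sided) to 0.60 (two-sided) for three levels with equal margins, roughly 0.55 to 0.64 under other margins and prevalences, and about 0.78 to 0.83 for a two-level kappa at 2.1%. Nor does it hold if sensitivity and specificity are exactly 0.8 at both cumulative cut-offs, where three-level kappa lies between 0.21 and 0.43.

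The conclusion rests on the large-sample variance, n = 750 and the assumed 82.9/15.0/2.1% split. That no alternative is named needs no assumption. The point should be corrected because this is the only power figure for the second primary aim; it does not affect the sample size.

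**What to change.** 1. Restate the power for the hypotheses as written, naming the alternative kappa, the number of categories, both sets of margins and the sidedness. Reconcile sidedness with Protocol 9.4, and the status of the test with SAP 1.2. Alternatively, replace the sentence with expected precision: a 95% half-width of about 0.08 for a three-level kappa of 0.40 to 0.60, or about 0.20 to 0.22 if a two-level kappa at 2.1% is meant.
2. Report testing-set sensitivity, specificity, PPV and NPV with exact intervals at each selected cut-off. The counts are already in planned Table 4.1, but the planned Aim 2 tables (4.1 to 4.8) do not list these measures, although the cut-points are chosen on them in training. A kappa below 0.40 would then not be read on its own as failure.

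The cost is SAP wording and one derived table, with no new data and no change in sample size. The downside is a less favourable stated power and visibly wide intervals for the high-risk group: 750 × 0.021 is about 16 people, and a sensitivity of 13/16 has an exact 95% interval of 0.54 to 0.96.
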